- **Aim 3**: To explore the impact of digital CBT-I on birth outcomes. In response to research indicating that insomnia and poor sleep quality are associated with increased risk for preterm birth, we will compare rates of preterm birth, as well as other birth outcomes such as low birthweight, delivery method, and APGAR scores, between digital CBT-I and TAU participants. Because the sample size of the proposed study will be too small to draw conclusions, this aim is exploratory.

Trial Design

The study is a parallel group, superiority, randomized controlled trial of digital CBT-I versus TAU among pregnant women, with a 1:1 allocation ratio.

Methods

Participants, interventions, and outcomes

Study setting. All study activities will occur remotely via phone, website, and digital app.

Eligibility criteria. Inclusion criteria are: 1) self-reported pregnancy up to 28 weeks gestation, 2) 18 years of age or older, 3) meets DSM-5 criteria for insomnia disorder as determined by the Sleep Condition Indicator (women experiencing symptoms \geq 1 month are eligible in contrast to DSM-5 criteria requiring symptom duration \geq 3 months) or experiencing elevated insomnia symptom severity as determined by a total score \geq 11 on the Insomnia Severity Index, and 4) has regular access to a web-enabled computer, tablet, or smart phone. Exclusion criteria are: 1) probable major depression as determined by a total score \geq 15 on the Edinburgh Postnatal Depression Scale (EPDS), 2) self-reported bipolar disorder, 3) self-reported history of psychosis, 4) active suicidality defined as scoring > 1 on EPDS item 10, or report of a specific suicide plan or recent attempt, and 5) shift work employee.

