Randomization. Upon the participant's completion of the baseline measures, study staff will request the condition assignment from the independent investigator who generated the randomization sequence. Study staff will inform participants of their condition assignment by phone call and email.

Follow-up assessments. Participants will complete all study measures and the daily sleep diaries at 10-weeks post-randomization, and all study measures at 18-weeks post-randomization, 36 weeks gestation, 3 months postpartum, and 6 months postpartum.

Sample size. Existing literature comparing CBT-I to treatment as usual suggests a large effect size (Cohen's d=0.95) for baseline to post-intervention differences and a medium effect size (Cohen's d=0.69) for baseline to 8-week follow-up on sleep efficiency.¹³ As for depression symptom severity, existing literature comparing CBT-I to treatment as usual suggests a small to medium effect size (Cohen's d=0.20-0.69) for baseline to post-intervention differences and a medium effect size (Cohen's d=0.48-0.78) for baseline to 8-week follow-up.^{9,14} Using G*Power for an ANOVA repeated measures with a within-between interaction, we estimated that 128 women were required to have 80% power to detect a small-to-medium effect size (Cohen's d=.30) with α =.01 for a within-between interaction. Attrition in web-based CBT-I programs ranges from 4-22%.^{13,16,17} but a meta-analysis of computer-based treatments for depression estimated drop-out rates of 38.4% in programs that offer administrative support. ¹⁸ We used the higher attrition estimate of 38%, yielding a required sample size of 208 participants (n=104 per group).

Recruitment. We will utilize several recruitment methods to meet our target sample size. Although recruitment will focus mainly on the Bay Area, participants can enroll from anywhere because all study activities are completed remotely.

UCSF Outpatient Recruitment Program. Study recruiters will review medical records of women receiving prenatal care at UCSF. Women who may be eligible based off chart review (e.g., less than 28 weeks pregnant) will be approached in the clinic waiting area at the time of their appointment to be introduced to the study. Recruiters will give the patient an opt-in card

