Electronic health record recruitment. MyChart (APeX) will conduct a search for patients based on the study's inclusion and exclusion criteria. This is a completely computer-aided search, meaning the computer— not a person— searches patient charts. When a patient is identified as potentially eligible, they will receive an email from MyChart that asks them to log in to MyChart to read about a study in which they might be interested. The email is short and is the same for every recipient—it contains no patient-specific or study-specific information. When the patient logs into MyChart, there will be a "Research" tab with template information about research participation and how to opt out of receiving recruitment messages. The patient can click through to learn about the specific study to which they have been matched. The patient has the option of clicking a button to let the study team know that they are interested in learning more about the study. The study team will only receive information about the patient if the patient takes this action. If the patient clicks "No thanks" or simply does not respond, they will not be contacted by the study team or receive any follow-up emails from MyChart about the study, nor will their information be shared with the study team.

Assignment of interventions

Allocation. The blocked randomization sequence will be generated by an independent investigator using Sealed Envelope.²⁰ The randomization sequence and block sizes will be concealed from study staff. The randomization sequence will be kept on an electronic file inaccessible to the study staff. Once a participant completes baseline measures, study staff will request the allocation assignment from the independent investigator. Study investigators and staff will not be able to influence randomization or have access to future allocations.

Blinding. For study administration purposes, staff will be unblinded to participant condition assignment after allocation. Study staff will be blinded to outcomes during the trial. Participants will be unblinded to condition assignment due to the nature of the comparison group, which is not an active comparator. The study statistician will remain blinded to condition assignment for all primary analyses.

Data collection, management, and analysis

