Mental health outcomes. Depressive symptom severity will be assessed using the Edinburgh Postnatal Depression Scale (EPDS).²⁵ The EPDS is a 10-item self-report measure that omits depressive symptoms that can be conflated with normal pregnancy symptoms (e.g., appetite disturbance). It is frequently used to assess depressive symptom severity during pregnancy. Total scores range from 0-30, with higher scores indicating higher symptom severity. Scores of 10 or greater suggest minor depression, and scores of 15 or greater suggest major depression among pregnant women.²⁶ Anxiety symptom severity will be assessed using the Generalized Anxiety Disorder Scale (GAD-7).²⁷ Scores range from 0-21 with higher scores indicating higher anxiety symptom severity. Scores of 0-4 suggest minimal anxiety, 5-9 suggest mild anxiety, 10-14 suggest moderate anxiety, and 11-21 suggest severe anxiety.

All study measures will e self-report and collected via online survey systems. With the exception of the sleep diaries, which will be collected via REDCap, study measures will be administered via Qualtrics.

Use of non-study treatments. At each follow-up assessment, participants will be asked about their use of the following aids to improve sleep: sleep medication prescribed by a doctor; combination sleep aid and pain reliever; over-the-counter or store-bought sleep aid; alternative therapy or herbal supplement; therapy or counseling; alcohol, beer, or wine; eyemask or ear plugs; other. Participants were also asked about their use of the following aids to improve mood: antidepressant medication, therapy or counseling; support group; alternative therapy or herbal supplements; other. Response options are 'rarely or never,' 'a few nights a month,' 'a few nights a week,' and 'every night/almost every night.'

Obstetric outcomes. Obstetric outcomes will be assessed via medical record review, and include but are not limited to the following outcomes: gestational age at delivery, APGAR scores, birthweight, and delivery method. Participants will also self-report birth outcomes in case we are not able to obtain their medical record data.^{28,29}

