Participants will be sent reminders via their preferred method of communication after 3, 5, and 10 days of non-response. After 2 weeks of non-response, we will contact their secondary contact person. After 3 weeks of non-response, we will mail the primary outcome measure with a stamped and addressed return envelope. Every effort will be made to obtain outcome data from

participants who discontinue the intervention. If need be, participants who discontinue the intervention can opt to only complete the primary outcome measure to reduce time burden.

Data management. Qualtrics maintains data behind a firewall. All data is accessed only by the owner of the survey who must provide a user ID and a password. All pieces of data are keyed to that owner identification and cannot be accessed by anyone else.

REDcap is housed in a locked and guarded data center staffed at all hours. Entrance to the data center requires use of a card key to unlock the data center door and a second card key lock secures the cage that the servers reside within. The security of the data center is further protected by an Operations desk that is staffed 24x7 and by a security camera system. REDcap servers are guarded by multiple firewall and intrusion detection systems. All electronic connections to the REDcap environment are encrypted. The REDcap production system is comprised of a web server front-end and a MySQL database server back-end. The web server resides in a demilitarized zone to ensure that survey participants are able to access REDcap surveys from any device connected to the Internet. The MySQL server back-end resides in the protected ISU subnet that is protected by UCSF maintained firewalls. The data stored in the REDcap MySQL database server can be accessed by the REDcap end users by logging in and opening the REDcap project(s) that they have been granted access to by the owners of the projects. Only ITS and ISU system administrators are authorized to access the back-end database server directly by logging into the virtual private network for the database server resides in.

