Statistical methods. Independent samples t-tests and chi-square tests will be used to examine between-group differences in baseline sociodemographic and clinical characteristics. Linear mixed effects models will be used to examine whether within-woman changes in sleep and mental health outcomes differ between the digital CBT-I and treatment as usual groups. 30 Models will include the sleep and mental health outcomes as the dependent variables, along with time, intervention group, and time by group interactions as the predictors. The models also will include random intercepts to accommodate the correlation among the repeated responses within women. The regression coefficients of time by intervention group interactions measure the differences in the rate of within-woman change in the outcomes between the two intervention groups. We will assess the statistical significance of the time by intervention group interaction using likelihood ratio tests. The primary analysis will assess differences in changes in insomnia symptom severity from baseline to post-intervention with time measured in weeks. Secondary analyses of additional sleep and mental health outcomes will use the same time scale. Additionally, we will examine change from baseline to follow-up.

Monitoring

Harms. Adverse events that are spontaneously reported by participants will be characterized by an independent safety officer as unexpected or expected, and causes will be characterized as definitely related, probably related, possibly related, or unrelated to study participation. Adverse events that are determined to be unrelated to study participation are documented but not reported to the IRB. All other adverse events are reported to the IRB.

Ethics and Dissemination

Research ethics approval

The research protocol will be submitted to the UCSF institutional review board for approval.

Protocol amendments

Protocol modifications will be communicated to all study investigators and approved by the IRB prior to implementation, and the trial registry will be updated accordingly.

Consent or assent

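### A follow-up EPDS item 10 answer above 1 is assigned to no one for review and falls outside the harms record, which takes only spontaneous reports

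*Combined protocol and SAP*

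**What the plan says.** Under Eligibility criteria, the protocol excludes women with "active suicidality defined as scoring > 1 on EPDS item 10, or report of a specific suicide plan or recent attempt". This stands as its own exclusion, next to a separate one for an EPDS total of 15 or more.

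The 10-item EPDS is also the measure of depressive symptom severity, a secondary outcome. Follow-up assessments schedules every study measure at 10 weeks after randomisation, "and all study measures at 18-weeks post-randomization, 36 weeks gestation, 3 months postpartum, and 6 months postpartum". Collection is by self-report at a distance: "With the exception of the sleep diaries, which will be collected via REDCap, study measures will be administered via Qualtrics".

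The Harms text under Monitoring opens: "Adverse events that are spontaneously reported by participants will be characterized by an independent safety officer as unexpected or expected". The officer also classifies causality, and events not judged unrelated go to the IRB.

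Two other rules bear on who would see an answer. Blinding states: "Study staff will be blinded to outcomes during the trial". Data management says of Qualtrics: "All data is accessed only by the owner of the survey who must provide a user ID and a password". Confidentiality adds that stored electronic data can be reached by the PI and trained researchers.

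**The concern.** The protocol treats one questionnaire answer as serious enough to keep a woman out of the trial. It then asks the same question repeatedly after randomisation without saying what happens if she gives that answer. Two things are at stake.

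The first is patient safety. A woman may disclose suicidal thoughts on a web form, and the plan names nobody who must read the answer.

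The second is the completeness of the harms record. Unless she also volunteers the matter as an event, the answer is not counted as a harm. The planned EPDS analysis compares symptom severity and would not bring it to light.

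**Working it through.** The plan states no figure on this point, so the check is a comparison of sections.

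1. **Is item 10 collected after entry?** Yes. The outcome measure is the 10-item EPDS, so item 10 is included, and all study measures are repeated at 10 weeks, 18 weeks, 36 weeks gestation, and 3 and 6 months postpartum. That is up to five occasions. Some women may have fewer. If randomised at 18 weeks gestation, the 18-week and 36-weeks-gestation visits coincide (18 + 18 = 36). If randomised at 26 weeks, the 10-week visit does (26 + 10 = 36). A birth before 36 weeks removes that visit.

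2. **Does the harms rule reach a positive answer?** No. The rule is limited to spontaneous reports, and a reply to a scheduled question is solicited.

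3. **Does any other section assign its review?** None in the supplied text. Item 10 and suicidality are mentioned only in the exclusion criteria. The survey owner, the PI and trained researchers have access to data, but access is not a duty to look, and no time limit or action is given. All study activities are remote, so the plan contains no clinic visit at which a positive answer would be noticed.

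4. **Would the EPDS total stand in for item 10?** No. The total runs from 0 to 30 over 10 items. If items are scored equally (an assumption), each contributes at most 30 / 10 = 3 points. A reply of 2 or 3 on item 10 is compatible with a low total, and a comparison of mean severity would not isolate it. The protocol's separate entry criteria for the total and for item 10 already recognise this.

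5. **Are spontaneous reports gathered evenly?** Not necessarily. Under Interventions, staff contact digital CBT-I participants who have not logged on or have fallen behind. No equivalent contact is described for TAU. Opportunities to volunteer an event may therefore differ by arm, whereas item 10 is put to both arms in the same way.

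Taken together, the stated rules leave a follow-up item 10 answer above 1 with no assigned reviewer and no place among the harms.

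**The case against.** The strongest reply is that this argues from silence in an incomplete file. The consent pages are not in the supplied text, and Consent or assent says the second form covers the remaining study procedures. A rule on distress answers could well sit there or in the IRB papers. This stands as a limit: a reader might infer that the trial had no suicide-risk procedure, and the documents do not support that. They show only that the protocol does not state or cite one. The limit leaves the scope of Harms as written, which excludes solicited answers.

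Other stronger readings also go too far:

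- **Blinding means nobody could see the answer.** The sentence covers study staff and does not name investigators, and other roles have data access. What is missing is a duty to review. It is also unclear that the independent safety officer is blinded at all, so the exemption proposed below is a clarification.
- **The ancillary-care statement shows the gap was intended.** That sentence concerns care and compensation for harm. It says nothing about reviewing or escalating answers.
- **Women multiplied by visits gives the size.** That counts questionnaires, not positive answers, and so does not measure risk.

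It is also fair to say that the entry exclusions (high EPDS total, active suicidality, bipolar disorder, history of psychosis) lower the expected frequency, and that TAU participants may seek any outside treatment. Neither replaces a review rule. Finally, item 10 above 1 is the protocol's entry cut-off and not a defined follow-up harm. Using it at follow-up is a proposal, though one that borrows the protocol's own threshold.

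**Conclusion.** The point holds as an omission in the supplied protocol. A follow-up EPDS item 10 score above 1 is neither assigned for review nor counted as a harm, although the same score is called active suicidality at entry. This is more than missing detail, because everyone could follow the stated rules and the answer would still go unread and unrecorded.

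Its size in women or in days of delay cannot be derived from the documents, and none is assumed. Its scope is both arms at up to five follow-ups. The conclusion rests on the supplied text being the whole of the plan's harms provisions. If a procedure exists elsewhere, what remains is the lack of a cross-reference and of a rule for recording these answers. The primary ISI analysis and the sample size are not affected.

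**What to change.** **Harms.** Add that a follow-up EPDS item 10 score above 1, in either arm, is flagged automatically to the existing independent safety officer for prompt review. The investigators and IRB should set the time limit and the clinical response, including who contacts the woman. If a procedure already exists, cite it. Record these answers as solicited safety events, kept apart from spontaneous reports, and tabulate them by arm. The denominator should be the number who answered item 10, because women who discontinue the intervention may give only the primary measure and persistent non-responders are mailed only that measure.

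**Blinding and Data management.** State that this review is exempt from outcome blinding and from the owner-only access rule.

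**Cost.** A few sentences, a survey flag, one descriptive table from data already collected, some safety-officer time and an IRB modification. The contact plan must work at a distance, since "participants can enroll from anywhere because all study activities are completed remotely". Referrals could have a small effect on later EPDS scores, a secondary outcome. Protocol Amendments records 183 of 208 women randomised by March 27, 2018, so a flag added to this version would protect only the follow-ups still to come. The table could cover earlier visits too, provided item-level answers were kept.
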